#### Dose limiting toxicity for Component 2 is defined as:

Component 1 dose limiting toxicity is defined any of the following events within 28 days after the FT596 dosing based on CTCAE v5:

- Grade 4 hematologic toxicity lasting > 7 days (not including lymphopenia)
- Grade 4 non-hematologic toxicity
- Grade ≥3 FT596 Infusion Related Reaction
- Grade 2 acute GVHD that requires steroid therapy >7 days or progression after 3 days of steroids or has partial response after 14 days of treatment
- Grade ≥3 acute GVHD
- Grade 4 cytokine release syndrome (CRS)
- Grade 3 CRS that does not resolve to < Grade 2 in 72 hours
- Grade 3 neurotoxicity
- Grade 3 organ toxicity involving vital organs; cardiac, central nervous system and pulmonary that lasts longer than 7 days including Grade 3 Investigations (laboratory values) of any duration that indicate damage to vital organs.
- Any Grade 3 non-hematological toxicity that does not resolve to ≤Grade 2 within 72 hours; excepting Grade 3 renal and hepatic toxicity which may take up to 7 days to resolve to ≤Grade 2
- Non-engraftment by Day 28 post-transplant

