The MTD will be determined by using a modified Continual Reassessment Method (CRM). (Goodman 1995) The CRM uses a power model for the probability of DLT at each dose, where the probability of toxicity at dose i is modeled as  $piexp(\alpha)$  where pi is a constant and  $\alpha$  is distributed a priori as a normal random variable with mean 0 and variance 2. The goal of this CRM will be to identify one of the 3 dose levels corresponding to the desired maximum acceptable toxicity rate of ≤25%.

Initial estimates of toxicity or the "skeleton" estimates are provided by the clinician. The initial estimates or prior probability of toxicity are listed as 1%, 3%, and 6% for doses 1, 2 and 3, respectively. As the study progresses, the CRM will continually update the estimates of the toxicity probabilities.

Patients are enrolled in cohorts of 3 starting at Dose Level 1. A minimum of 28 days will separate each cohort. For Dose Level 1 a minimum of 28 days will separate each patient to assess for dose limiting toxicity (DLT). In subsequent cohorts, the 1st and 2nd patient will be separated by at least 28 days and at least 14 days will separate the 2nd and 3rd patient. Enrollment will continue in cohorts of 3 and each new cohort of 3 will be sequentially assigned to the most appropriate dose based on the updated toxicity probabilities after the 3rd patient from the previous cohort has reached 28 days. The MTD will be identified when the total sample size of 18 is exhausted or 6 patients are sequentially enrolled at the same dose. A maximum of 18 patients is used in part due to low expected toxicity. The function 'crm' from the R package 'dfcrm' will calculate posterior means of toxicity probabilities. The CRM uses a Bayesian framework that combines experience from patients in the earlier part of the trial with the clinician's initial best estimate of the toxicity rates at each dose level to estimate a dose level that best corresponds to the target toxicity of ≤25%. Dose escalation of more than one level is not permitted with this design.

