Component 2 will use a similar design but identify the MTD of FT596 when given as a single dose at Day 7. Up to two dose levels of FT596 are planned (1 Dose Level below the MTD from component 1 and the MTD from component 1) so any two sequential dose levels of the following may be included (Dose Level -1:  $3x10^7$  cells/dose, Dose Level 1:  $9x10^7$  cells/dose, Dose Level 2:  $3x10^8$  cells/dose, Dose Level 3:  $9x10^8$  cells/dose).

The DLT events for Component 2 are the same as in Component 1 except for the addition of:

• Non-engraftment by Day 28 post-transplant

The MTD will be identified in the same fashion as Component 1 except that the initial estimates or prior probability of toxicity may be slightly higher due to the infusion of cells at Day 7 plus the additional possible DLT event. Assuming that we start at Dose Level 2, the skeleton probabilities might be listed as 5% and 10% for doses 2 and 3, respectively. The target toxicity level will still be  $\leq 25\%$ . As in Component 1, the CRM will continually update the estimates of the toxicity probabilities of both doses; first at the end of 28 days post infusion for each of the first three patients; and at the end of the of 28 day follow-up for the last patient in each of the 3 patient cohorts beyond the initial 3 patients. A minimum of 28 days will separate each patient in the 1st cohort to assess for dose limiting toxicity (DLT). In subsequent cohorts, the 1st and 2nd patient will be separated by at least 28 days and at least 14 days will separate the 2nd and 3rd patient.

As in Component 1, each new cohort of three patients will be sequentially assigned to the most appropriate dose based on the updated toxicity probabilities, and the MTD will be identified when a total sample size of 18 is exhausted or 6 patients are sequentially enrolled at the same dose.

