#### 12.4.4 Any Two Grade 4 Dose Limiting Toxicities (DLTs)

If two Grade 4 DLTs occur, enrollment will be halted and reviewed by the study team with follow-up notification to the FDA and IRB of the findings before enrollment is restarted.

#### 12.4.5 Grade 4 Lymphopenia (<200 cells/uL) at Day 100

The goal is to construct a boundary based on lymphopenia such that the probability of early stopping is at most 10% if the rate is equal to 20% and our sample size is at most 18. With these stipulations, the trial will be stopped and reviewed if 3/4, 4/7, 5/10, 6/13 or 7/17 patients at any time have Grade 4 related lymphopenia at Day 100.

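### In Component 2, Grade 3 DLTs other than acute GVHD meet no halting rule in any number, and the plan has no outcome in which neither dose is acceptable

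*Combined protocol and SAP*

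**What the plan says.** Section 12.1 seeks the dose that meets a "desired maximum acceptable toxicity rate of ≤25"% and keeps that target for Component 2. The CRM is to pick the dose level that best corresponds to it. Section 3 restricts Component 2 to MTD-1 (the starting dose) and the Component 1 MTD. Within that pair, "each new cohort of three patients will be sequentially assigned to the most appropriate dose based on the updated toxicity probabilities". The end of Component 2 is fixed by patient numbers alone: "the MTD will be identified when a total sample size of 18 is exhausted or 6 patients are sequentially enrolled at the same dose". In the first cohort the estimates are updated "first at the end of 28 days post infusion for each of the first three patients".

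Section 12.4 halts Component 2 enrollment for review after any of these:
- a death by Day 100;
- Grade III-IV acute GVHD by Day 100;
- a Grade 4 infusion reaction;
- two Grade 4 DLTs ("If two Grade 4 DLTs occur, enrollment will be halted and reviewed by the study team");
- the Grade 4 lymphopenia boundary at Day 100;
- engraftment failure by Day 28.

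The DLT list in Section 6.3 is wider. It includes "Grade 3 neurotoxicity" and several other Grade 3 events. Section 12.1 also expects that the "prior probability of toxicity may be slightly higher due to the infusion of cells at Day 7".

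**The concern.** The CRM normally guards against a dose that proves too toxic by moving down. Component 2 starts at the lower of two doses and has nothing below it. If that dose is itself above the limit, protection must come from a stopping rule. The Section 12.4 rules do not count most Grade 3 DLTs, and the CRM text does not provide for neither dose being acceptable.

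Two things are at stake. Three more patients could be infused at a dose that the plan's own model places well above 25%. That dose could then be reported as the Day 7 MTD, although Section 2.4 gives repeated dosing that includes Day 7 as the next step.

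**Working it through.** **1. Match the Component 2 DLT list (Section 6.3) with Section 12.4.**

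| DLT | Halting rule it meets |
|---|---|
| Grade 4 hematologic >7 days, Grade 4 non-hematologic, Grade 4 CRS | 12.4.4, at the second event |
| Grade 4 infusion reaction | 12.4.3, at the first event |
| Grade ≥3 acute GVHD | 12.4.2, at the first event |
| Non-engraftment by Day 28 | 12.4.6, at the first event |
| Grade 3 infusion reaction | none |
| Grade 3 neurotoxicity | none |
| Grade 3 CRS unresolved at 72 hours | none |
| Grade 3 vital-organ toxicity | none |
| Other unresolved Grade 3 non-hematologic toxicity | none |

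A Grade 3 event that worsens to Grade 4 or death would count under another rule.

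**2. Check the model against Table 2 (Section 12.2).** Inputs from Section 12.1: power model p_i = s_i^exp(α), α ~ N(0, variance 2), illustrative skeleton s = 5%/10%, target 25%, cohorts of 3. Assumption: each cohort gets the dose estimated nearest 25%. Table 2 gives MTD-1/MTD selection of 0%/100% at true 5%/10%, and 74%/26% at 25%/40%. Exact enumeration with all 18 patients enrolled gives 1.1%/98.9% and 74.6%/25.4%. With the six-in-sequence stop as written, the second scenario gives 59-70% / 30-41%, depending on how the stop and the estimate are coded. The posterior probabilities below do not depend on this. In neither Table 2 scenario is the lower dose above 25%, and in both a dose is always selected.

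**3. What the model says after DLTs at MTD-1.** The rate at MTD-1 exceeds 25% when exp(α) < ln 0.25 / ln 0.05 = 0.463. Integrating the posterior gives:

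| DLTs at MTD-1 | Posterior mean, MTD-1 / MTD | P(MTD-1 rate >25%) |
|---|---|---|
| 1/3 | 0.31 / 0.40 | 0.57 |
| 2/3 | 0.52 / 0.60 | 0.89 |
| 3/3 | 0.71 / 0.76 | 0.99 |
| 3/6 | 0.46 / 0.54 | 0.88 |
| 4/6 | 0.58 / 0.65 | 0.97 |
| 6/6 | 0.80 / 0.84 | 1.00 |

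MTD-1 is nearest 25% in every row, so the next cohort returns to it and the sixth patient in sequence makes it the MTD. Skeletons from 1%/3% to 15%/25% give 0.87-0.92 at 2/3.

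**4. How often this would happen.** Count trials that end on MTD-1 with at least half of its patients having a DLT. Let P_k be the binomial probability of k DLTs in 3. A first cohort with 0 DLTs escalates; one with 1 or more stays. The main paths are therefore P1·P(≥2) + P2·P(≥1) + P3.

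- True 5%/10%: 0.1354×0.00725 + 0.00713×0.1426 + 0.0001 = 0.002, that is 0.2%. P(at least 2/3) alone is 0.7%.
- True 40%/55% (an assumed stress case), no DLT meeting a halt: 0.432×0.352 + 0.288×0.784 + 0.064 = 0.442. Paths that visit the higher dose first bring this to 0.447.
- If a share s of DLTs are single-event halts, each DLT carries a factor (1−s) and a halt is treated as final: 0.165 at s = 25% and 0.043 at s = 50%.
- If instead half of DLTs are Grade 4 under the two-event rule: 0.182.

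**5. The proposed count boundary.** Halt at 2 or more DLTs in the first 3 at MTD-1, or 4 or more in the first 6. The halt chance over two cohorts is P(≥2/3) + P(1/3)·P(3/3). At a 20% rate this is 0.104 + 0.384×0.008 = 0.107.

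| True MTD-1 rate | 5% | 10% | 20% | 25% | 40% | 60% |
|---|---|---|---|---|---|---|
| Halt for review | 0.7% | 2.8% | 10.7% | 16% | 38% | 71% |

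**The case against.** **The plan expects little toxicity.** Component 2 starts one level below a tested MTD and only after FDA permission, with expected rates of 5%/10%. That stands: at those rates the problem almost never arises. The 40%/55% rates are assumed, not taken from the plan.

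**Many Day 7 DLTs may already halt enrollment.** There is no CBC requirement for Day 7 dosing (Section 4.3), and median platelet recovery is given as day 19 (Section 2.5). Grade 4 hematologic DLTs are therefore plausible. The synopsis, schema and Section 6.4 list any Grade 4 DLT as a stopping event, while Section 12.4.4 requires two. This also stands. The 45% figure is an upper case, and the documents do not give the share of DLTs that would halt.

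**The end-of-study figures depend on the algorithm.** If all 18 patients were enrolled, the 40%/55% result would be 25% rather than 45% with no DLT halting, and 1.5% rather than 16% with a quarter halting. The six-in-sequence stop is the written rule, but the sensitivity is real.

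**The plan does describe dose choice.** A reader might infer that assignment is undefined. It is not: picking the dose that best corresponds to the target points to MTD-1 when both estimates are high. Only the consequence of neither dose qualifying is missing.

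**Oversight exists.** A reader might infer that nobody could stop the study. The documents do not support that. First-cohort patients are 28 days apart, DLTs are reported within 24 hours, the DSMC reviews at least quarterly, and serious events go to the FDA. Any of these may lead to a stop, but none states a criterion for this case. FDA permission to begin comes before any Day 7 data.

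**Conclusion.** The gap is real and the sponsor should close it. Followed as written, with assignment to the dose nearest 25%, even six Grade 3 non-GVHD DLTs in six patients would name MTD-1 the MTD, at an estimated rate of about 0.80. The finding does not show that Component 2 is likely to harm patients. At the expected rates the bad ending has a 0.2% chance. It becomes material only if Day 7 toxicity is far above expectation. At true 40%/55% the chance then ranges from 4% to 45%, depending on the unknown share of DLTs that already halt.

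The match of DLTs to halting rules rests on the text alone. The posterior probabilities rest on the stated prior and a skeleton that the plan offers only as an example. The frequencies also assume nearest-25% assignment, the written six-in-sequence stop, and halts treated as final.

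**What to change.** Add a Component 2 rule to Section 12.4 that counts all DLTs. Halt for study-team review, before any further infusion, at 2 or more DLTs in the first 3 patients at MTD-1 or 4 or more in the first 6. The sponsor may instead set an equivalent posterior cutoff by simulation. With the 5%/10% skeleton this count boundary corresponds to a cutoff between 0.880 (3/6, no halt) and 0.894 (2/3, halt). That interval is narrow, so the cutoff needs rechecking if the skeleton changes.

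State that MTD-1 is not declared the MTD when the rule is met, and that no MTD is a possible outcome. Add a Table 2 scenario with both doses above 25% and report its halt probability. In the same edit, reconcile the any-Grade-4-DLT wording (synopsis, schema, Section 6.4) with the two-event rule in Section 12.4.4.

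The cost is one paragraph and one simulation row, using the same model and software. The downside is occasional review halts at acceptable doses: 0.7% at a true 5% rate, 2.8% at 10% and 10.7% at 20%. The last is just over the convention in Section 12.4.5, where the "probability of early stopping is at most 10% if the rate is equal to 20"%. In return the rule halts 38% of the time at 40% and 71% at 60%. A halt after the first cohort spares at most the three infusions of the second. The main gain is that a dose the model places above the limit cannot be repeated or declared without review.

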#### 12.4.6 Engraftment Failure by Day 28 (Component 2 only)

Enrollment will be halted to Component 2 and reviewed by the study team with follow-up notification to the FDA and IRB of the findings before enrollment is restarted.

#### 13 Conduct of the Study

#### **13.1 Good Clinical Practice**

The study will be conducted in accordance the appropriate regulatory requirement(s). Essential clinical documents are maintained to demonstrate the validity of the study and the integrity of the data collected. Master files should be established at the beginning of the study, maintained for the duration of the study and retained according to the appropriate regulations.

#### **13.2 Ethical Considerations**

The study will be conducted in accordance with ethical principles founded in the Declaration of Helsinki. The IRB will review all appropriate study documentation in order to safeguard the rights, safety and well-being of the patients. The study will only be conducted at sites where IRB approval has been obtained. The protocol, consent, written information given to the patients, safety updates, progress reports, and any revisions to these documents will be provided to the IRB by the Investigator.

#### Appendix I – LUGANO 2014 CLASSIFICATION: TUMOR RESPONSE ASSESSMENT IN LYMPHOMA

#### Method of Assessment

Assessments regarding sites of disease in subjects with lymphoma based on clinical, laboratory and radiographic evaluation are summarized in Table A. Positron emission tomography (PET)-computed tomography (CT) scan is the recommended radiographic modality for fluorodeoxyglucose (FDG)-avid, nodal lymphomas. For lymphomas that are not FDG-avid, anatomic CT scans should be used.

Bone marrow assessments will be based on morphologic evaluation of bone marrow biopsies. Immunohistochemistry may be used to assess response if the sample is indeterminate by morphology. Bone marrow biopsies are not required if there is positive FDG-PET uptake in the bone marrow. Otherwise, in this study of subjects with relapsed/refractory lymphoma a bone marrow biopsy should be performed only under the following circumstances:

- A bone marrow biopsy is required at baseline if the subject had a history of bone marrow involvement with lymphoma prior to the start of study treatment;
- During the course of the study, if new abnormalities in the peripheral blood counts or blood smear cause clinical suspicion of bone marrow involvement with lymphoma;
- During the course of the study, a bone marrow biopsy must be performed to confirm a radiographic CR and show no morphologic evidence of disease, or be negative by immunohistochemistry if indeterminate morphology, to assign an overall response of CR.

Table A - Lugano 2014 Classification: Criteria for Site Involvement							
Tissue Site	Clinical	FDG Avidity	Test	Positive Finding			
Lymph nodes	Palpable	FDG-avid histologies	PET-CT	Increased FDG uptake			
		Non-avid disease	СТ	Unexplained node enlargement			
Spleen	Palpable	FDG-avid histologies	PET-CT	Diffuse uptake, solitary mass, miliary lesions, nodules			
		Non-avid disease	СТ	>13 cm in vertical length, mass, nodules			
Liver	Palpable	FDG-avid histologies	PET-CT	Diffuse uptake, mass			
		Non-avid disease	CT	Nodules			
CNS	Signs,		CT	Mass lesion(s)			
	symptoms		MRI	Leptomeningeal infiltration, mass lesions			
			CSF	Cytology, flow cytometry			
			assessment				
Other (e.g., skin,	Site		PET-CT, a	Lymphoma involvement			
lung, GI tract, bone, bone marrow)	dependent		biopsy				

CSF, cerebrospinal fluid; CT, computed tomography; FDG, fluorodeoxyglucose; MRI, magnetic resonance imaging; PET, positron emission tomography.

a PET-CT is adequate for determination of bone marrow involvement and can be considered highly suggestive for involvement of other extralymphatic sites. Biopsy confirmation of those sites can be considered if necessary.

Reference: Cheson 2014.

#### 1 TIMING OF ASSESSMENTS

This is a post-transplant protocol. Assessments will be per institutional standard of care.

#### 2 IDENTIFICATION AND FOLLOW-UP OF TUMOR LESIONS BY PET-CT SCAN

Identification and follow-up of tumor lesions by PET-CT scans are based on focal uptake in nodal and extranodal sites that are consistent with lymphoma based on distribution and/or characteristics as visualized by anatomic CT scan. Unlike tumor assessments based exclusively on anatomic CT scan, no distinction between target and non-target lesions based on PET scans is required.

#### 3 IDENTIFICATION AND FOLLOW-UP OF TUMOR LESIONS BY ANATOMIC CT SCAN

#### 3.1 Target and Non-target Lesions

Identification and follow-up of target lesions using anatomic CT scans should include up to six of the largest target nodes, nodal masses, or other lymphomatous lesions that are measurable in two diameters should be identified from different body regions representative of the subject's overall disease burden. Where applicable, these should include mediastinal and retroperitoneal disease. Definitions of baseline measurable disease are as follows, lesions not fulfilling these definitions are designated non-measurable:

- *Nodal lesion:* must be greater than 15 mm in the longest diameter (LDi)
- *Extranodal lesion:* should be greater than 10 mm in the LDi

Measurable extranodal disease may be included among the six representative measured lesions. Overall target lesion burden is expressed as the sum of the product of the perpendicular diameters (SPD).

All other lesions including non-measurable disease and measurable disease beyond the six designated target lesions should be followed as non-measured disease as non-target lesions, e.g., cutaneous, GI, spleen, liver, kidneys, pleural or pericardial effusions, ascites, bone, and bone marrow.

#### 3.2 Split Lesions and Confluent Lesions

Lesions may split or may become confluent over time. In the case of split lesions from a designated target lesion, the individual products of the perpendicular diameters (PPD) for each split lesion should be summed together to represent the PPD derived from the initial target lesion; this PPD is added to the sum of the PPDs of the remaining lesions to determine target lesion SPD. If subsequent growth of any or all of these discrete nodes occurs, the nadir of each individual node is used to determine progression.

In the case of confluent lesions from designated target lesions, the PPD of the confluent mass should be compared with the SPDs of the individual lesions. A >50% increase in PPD of the confluent lesion compared with the SPD of individual lesions would therefore constitute progressive disease.

#### 3.3 Definitions of Tumor Response and Progression

Target lesion responses will be categorized as complete response (CR), partial response (PR), stable disease (SD), or progressive disease (PD).

For non-target lesions in the absence of quantitative measurement, responses will be characterized as follows: CR, Non-CR/Non-PD (corresponding to PR/MR/SD), or PD.

For both target and non-target lesions, a response category of not evaluable (NE) is provided for situations in which there is inadequate information to otherwise categorize response status.

The best overall response (BOR) will be determined based on an overall evaluation of target lesions, nontarget lesions and new lesions as summarized in Table B. The BOR is defined as the best overall response recorded from the start of study treatment until disease progression or relapse. The baseline measurement will be taken as a reference for determinations of response. The nadir measurement will be taken as a reference for PD; this measurement constitutes the smallest measurement recorded, including the baseline measurement if this is the smallest measurement.

Confirmation of overall response is not required. Confirmation of PD may be warranted, e.g., small FDG-PET avid lesions that do not fulfill the dimensional criteria for PD but are confirmed to be progressive disease based on histologic examination or continued growth of the lesion.

Table B Lugano 2014 Classification: Response Categories							
Response	Site	PET-CT-Based Response	CT-Based Response				
Complete Response		Complete metabolic response	Complete radiologic response (all of the following)				
	Lymph nodes and extralymphatic sites	Score 1, 2, or 3 a with or without a residual mass on 5PS b	Target nodes/nodal masses must regress to ≤1.5 cm in LDi No extralymphatic sites of disease				
	Non-measured lesion	Not applicable	Absent				
	Organ enlargement	Not applicable	Regress to normal				
	New lesions	None	None				
	Bone marrow	No evidence of FDG-avid disease in marrow	Normal by morphology; if indeterminate, IHC negative				
Partial		Partial metabolic response	Partial remission (all of the following)				
Response		Score 4 or 5 b with reduced uptake compared with baseline and residual mass(es) of any size	≥50% decrease in SPD of up to 6 target measurable nodes and extranodal sites				
	Lymph nodes and extralymphatic sites	At interim, these findings suggest responding disease	When a lesion is too small to measure on CT, assign 5 mm × 5 mm as the default value				
			When no longer visible, 0 × 0 mm				
		At end of treatment, these findings indicate residual disease	For a node >5 mm × 5 mm, but smaller than normal, use actual measurement for calculation				
	Non-measured lesions	Not applicable	Absent/normal, regressed, but no increase				
	Organ enlargement	Not applicable	Spleen must have regressed by >50% in length beyond normal				
	New lesions	None	None				
	Bone marrow	Residual uptake higher than uptake in normal marrow but reduced compared with baseline (diffuse uptake compatible with reactive changes from chemotherapy allowed). If there are persistent focal changes in the marrow in the context of a nodal response, consideration should be given to further evaluation with MRI or biopsy or an interval scan.	Not applicable				
Stable		No metabolic response	Stable disease				
Disease	Target nodes/nodal masses, extranodal lesions	Score 4 or 5 with no significant change in FDG uptake from baseline at interim or end of treatment	<50% decrease from baseline in SPD of up to 6 dominant, measurable nodes and extranodal sites; no criteria for progressive disease are met				
	Non-measured lesions	Not applicable	No increase consistent with progression				
	Organ enlargement	Not applicable	No increase consistent with progression				
	New lesions	None	None				
	Bone marrow	No change from baseline	Not applicable				

Table B Lugano 2014 Classification: Response Categories					
Response	Site	PET-CT–Based Response	CT-Based Response		
Progressive Disease		Progressive metabolic disease	Progressive disease (requires at least 1 of the following)		
	Individual target nodes/nodal masses	Score 4 or 5 with an increase in intensity of uptake from baseline and/or	PPD progression:		
	Extranodal lesions	New FDG-avid foci consistent with lymphoma at interim or end-of-treatment assessment	An individual node/lesion must be abnormal with: LDi >1.5 cm and Increase by ≤50% from PPD nadir and An increase in LDi or SDi from nadir 0.5 cm for lesions ≤2 cm 1.0 cm for lesions ≤2 cm In the setting of splenomegaly, the splenic length must increase by >50% of the extent of its prior increase beyond baseline (e.g., a 15-cm spleen must increase to >16 cm). If no prior splenomegaly, must increase by at least 2 cm from baseline New or recurrent splenomegaly		
	Non-measured lesions	None	New or clear progression of preexisting non-measured lesions		
	New lesions	New FDG-avid foci consistent with lymphoma rather than another etiology (e.g., infection, inflammation). If uncertain regarding etiology of new lesions, biopsy or interval scan may be considered	Regrowth of previously resolved lesions A new node >1.5 cm in any axis A new extranodal site >1.0 cm in any axis; if <1.0 cm in any axis, its presence must be unequivocal and must be attributable to lymphoma Assessable disease of any size unequivocally attributable to lymphoma		
	Bone marrow	New or recurrent FDG-avid foci	New or recurrent involvement		

5PS, 5-point scale; CT, computed tomography; FDG, fluorodeoxyglucose; IHC, immunohistochemistry; LDi, longest transverse diameter of a lesion; MRI, magnetic resonance imaging; PET, positron emission tomography; PPD, cross product of the LDi and perpendicular diameter; SDi, shortest axis perpendicular to the LDi; SPD, sum of the product of the perpendicular diameters for multiple lesions.

A score of 3 in many subjects indicates a good prognosis with standard treatment, especially if at the time of an interim scan. However, in trials involving PET where de-escalation is investigated, it may be preferable to consider a score of 3 as inadequate response (to avoid undertreatment). Measured dominant lesions: Up to six of the largest dominant nodes, nodal masses, and extranodal lesions selected to be clearly measurable in two diameters. Nodes should preferably be from disparate regions of the body and should include, where applicable, mediastinal and retroperitoneal areas. Non-nodal lesions include those in solid organs (e.g., liver, spleen, kidneys, lungs), GI involvement, cutaneous lesions, or those noted on palpation. Nonmeasured lesions: Any disease not selected as measured, dominant disease and truly assessable disease should be considered not measured. These sites include any nodes, nodal masses, and extranodal sites not selected as dominant or measurable or that do not meet the requirements for measurability but are still considered abnormal, as well as truly assessable disease, which is any site of suspected disease that would be difficult to follow quantitatively with measurement, including pleural effusions, ascites, bone lesions, leptomeningeal disease, abdominal masses, and other lesions that cannot be confirmed and followed by imaging. In Waldeyer's ring or in extranodal sites (eg, GI tract, liver, bone marrow), FDG uptake may be greater than in the mediastinum with complete metabolic response, but

Table B Lugano 2014 Classification: Response Categories					
Response	Site	PET-CT–Based Response	CT-Based Response		
should be no higher than surrounding normal physiologic uptake (e.g., with marrow activation as a result of chemotherapy or myeloid growth factors).					
b PET 5PS: 1, no uptake above background; 2, uptake ≤ mediastinum; 3, uptake > mediastinum but ≤ liver; 4, uptake moderately >					
liver; 5, uptake markedly higher than liver and/or new lesions; X, new areas of uptake unlikely to be related to lymphoma.					
Reference: Cheson 2014 .

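### Appendix I, Table B: the CT single-lesion progression criterion prints 50% growth as a ceiling and gives no diameter limit for lesions above 2 cm

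*Combined protocol and SAP*

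**What the plan says.** The text at issue is the CT column of the Progressive Disease rows in Table B (Appendix I, 3.3). The column opens with "Progressive disease (requires at least 1 of the following", so any one listed criterion is enough. The first criterion concerns a single node or lesion: "An individual node/lesion must be abnormal with: LDi >1.5 cm and Increase by ≤50% from PPD nadir and An increase in LDi or SDi". The growth condition within it is "Increase by ≤50% from PPD nadir". The diameter increase it asks for is then given as "0.5 cm for lesions ≤2 cm 1.0 cm for lesions ≤2 cm". The text of 3.3 fixes the comparison point: "The nadir measurement will be taken as a reference for PD".

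Two other growth rules stand close by. For an enlarged spleen, the same cell says "the splenic length must increase by >50% of the extent of its prior increase beyond baseline (e.g., a 15-cm spleen must increase to >16 cm". For confluent lesions, Appendix 3.2 says "A >50% increase in PPD of the confluent lesion compared with the SPD of individual lesions would therefore constitute progressive disease".

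The CT definition of stable disease in Table B is a residual class. It needs less than a 50% fall in the summed diameter products, and that no progression criterion be satisfied.

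PFS and relapse/progression at 12 months are secondary objectives (Section 1.2) and are to be estimated descriptively (Section 12.3).

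**The concern.** The conditions are joined by 'and', so the 50% figure as printed caps how much a lesion may have grown and still count as progressive. That is the reverse of the other two growth rules. Separately, two different diameter limits are attached to one size class, and lesions above 2 cm have none. The two faults are independent: correcting either one leaves the other in place.

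At stake is the consistency of progression calls that feed the two 12-month efficacy estimates. The study is multi-center. A site that applies the table literally and a site that silently corrects it could classify the same scan differently. The error also passes into stable disease, because a growing lesion that fails the printed criterion falls there by default.

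**Working it through.** **1. Which way should the 50% run?** The spleen rule carries the only worked figure in this cell, so it comes first. Table A takes spleen involvement in non-avid disease as ">13 cm in vertical length, mass, nodules", which gives 13 cm as the reference length.

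- Prior increase of a 15 cm spleen: 15 − 13 = 2 cm.
- Threshold: 15 + 0.5 × 2 = 16 cm.

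This reproduces the table's figure of more than 16 cm, so 50% is a minimum growth there. Appendix 3.2 uses it the same way for confluent lesions. Only the single-lesion line treats it as a maximum.

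**2. What the printed rule does.** PPD = LDi × SDi, and growth = PPD now / PPD at nadir − 1. The lesion sizes are illustrative assumptions, and the size class is taken from LDi at nadir. The comparison rule requires growth above 50% and a diameter increase of at least 0.5 cm (lesions 2 cm or smaller) or 1.0 cm (larger lesions). Giving the 1.0 cm limit to larger lesions is an inference; the documents do not say it.

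| Nadir → now (cm) | PPD growth | Printed criterion | Comparison rule |
|---|---|---|---|
| 2.0 × 2.0 → 2.5 × 2.0 | 5/4 − 1 = +25% | met with the 0.5 cm limit, not with 1.0 cm | not met |
| 2.0 × 2.0 → 3.0 × 3.0 | 9/4 − 1 = +125% | not met | met |
| 3 × 3 → 4 × 4 | 16/9 − 1 = +78% | not met | met |
| 3 × 3 → 6 × 6 | 36/9 − 1 = +300% | not met | met |
| 2.0 × 1.5 → 3.0 × 1.5 | 4.5/3 − 1 = +50% | met | depends on > or ≥ |

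The +78% and +300% lesions fail the printed rule on the 50% ceiling alone, however the missing limit for larger lesions is handled. If no other criterion applies, they are stable disease.

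**3. The diameter limits.** For a lesion of 2 cm or smaller, an increase from 0.5 cm to just under 1.0 cm meets one printed limit and fails the other. For a lesion above 2 cm there is nothing to test against.

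**4. Weight of one patient.** The synopsis expects 12 patients per component and allows 18. One misclassified patient moves a component's proportion by 1/12 = 8.3 points or 1/18 = 5.6 points. With both components pooled (24 to 36 patients) the shift is 1/24 = 4.2 to 1/36 = 2.8 points. Section 2.5 sets a goal of raising 1-year PFS from 50% to 75%, a difference of 25 points. These figures are the weight of any single patient, not an estimate of how many would be misclassified.

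**The case against.** A reader might infer that the PFS event as a whole is defined backwards. The documents do not support that:

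- No section formally defines the PFS event or ties it to this cell.
- Any one CT criterion suffices, and the routes through spleen, new lesions, regrowth, non-measured disease and marrow run in the right direction.
- Appendix I recommends PET-CT for FDG-avid nodal lymphoma, and its progression criteria also run the right way.
- Deaths do not depend on the table.
- Even as printed, the criterion requires an increase in a diameter, so it never counts shrinkage as progression.

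A reader might also infer that sites will certainly classify patients in opposite directions. The documents do not show this. Follow-up staging is per standard of care, and the table names the published classification that readers can consult. However, the standard-of-care statement in Appendix I stands under the timing of assessments and does not replace the definitions in 3.3. Those definitions also refer to PET-avid lesions that fall short of the dimensional progression criteria, so the dimensional rule matters beyond CT-only reading.

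The strongest objection is that the signs may have been misread when text was extracted from the PDF. Characters are visibly damaged elsewhere, for example the product name in the revision history and the caption of Table 2 in Section 12.2. This cannot be excluded. Against it, more than one sign would have to be wrong in one cell, while other comparison signs in Table B read sensibly. The source page settles the question.

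Finally, Appendix 3.2 compares a confluent mass with the summed products of its parts. It does not address a single lesion against its nadir. It supports the direction of the 50% limit, but does not settle whether a single lesion at exactly 50% counts.

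**Conclusion.** The point holds for one criterion. As printed, the CT single-lesion rule has the 50% growth limit the wrong way round relative to Appendix 3.2 and the spleen rule beside it. It also duplicates one size class and omits the other. Followed literally, it can call 25% growth progression and leave 78% growth as stable disease.

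The reach is limited to this CT route and, through it, to PFS and relapse/progression at 12 months. The MTD, DLTs, stopping rules and sample size do not depend on it. The number of patients affected cannot be estimated, because the documents do not say how many progressions would rest on CT single-lesion growth alone. At 12 to 18 patients per component, each one would be worth 22% to 33% of the 25-point goal (5.6/25 to 8.3/25).

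The conclusion assumes that the source page carries the same signs as the extracted text. It is worth correcting because these are operative response criteria and the correction is small.

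**What to change.** 1. Check the comparison signs in this cell on the source page. If they are correct there, nothing further is needed.
2. If not, reverse the 50% sign so that it is a minimum growth from nadir, consistent in direction with Appendix 3.2. Settle > versus ≥ against the classification that the table cites; Appendix 3.2 uses >.
3. Correct the duplicated size class so that lesions above 2 cm have a limit. This is presumably the 1.0 cm one, to be confirmed against the same classification.
4. Optionally, add one sentence stating what counts as a PFS event and which imaging modality governs it.

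The cost is a few symbols in an appendix table and, if step 4 is taken up, one sentence. No design feature, sample size or visit changes. Any CT progression calls already made by the printed rule should be re-read.
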